1. PURPOSE OF THE STUDY

a. Brief Summary

The purpose of this study is twofold:

- (1) To evaluate the feasibility of a digital voice assistant to help patients manage insulin-dependent diabetes between routine clinic visits. Specifically, the custom app that we will develop will help patients log their blood sugars and medication use, as well as help them adjust their insulin dose based on a protocol that their physician prescribes.
- (2) To evaluate the effects of such an intervention on specific medical outcomes, such as medication adherence, blood sugar control and time to optimal insulin dose, as well as patient self-efficacy measures.

The digital voice assistant used will be an Amazon Echo Dot and it will use a custom application (app) to help patients manage their diabetes at home.

b. Objectives

We hope to learn whether a digital voice assistant can be reliably used by patients at home between clinic visits to improve management of insulin-dependent diabetes. We hope that this improved management will translate into improved medical outcomes. In the future, the findings of this study could serve as a first step towards developing an integrated outpatient solution that leverages voice assistant technology in the patient's home to improve management of multiple chronic medical conditions.

c. Rationale for Research in Humans

The purpose of this study is to test the efficacy of a digital voice assistant in individuals with insulin-dependent diabetes.

2. STUDY PROCEDURES

a. Procedures

Screening:

Our team will recruit patients with uncontrolled type 2 diabetes who are being started on insulin or who are already on insulin and having active adjustments to their dose. To identify patients that may be eligible for recruitment, our team will use STARR's cohort discovery tool to create a report of patients at four Stanford Internal Medicine clinic sites with type 2 diabetes and a recent hemoglobin A1c greater than 8%. Our team will then contact the primary care providers of these patients to ask them if they think their patients would benefit from inclusion in our study. The four Stanford Internal Medicine clinic sites are Stanford Internal Medicine East, Stanford Internal Medicine Los Altos, Stanford Internal Medicine Portola Valley and Stanford Internal Medicine Santa Clara.

Recruitment process: When an eligible candidate is identified per the screening process above, the research team will contact the patient's primary care physician and inform them of this study. If the patient's primary care physician agrees that the patient would benefit from inclusion in this study, they will reach out to the patient and describe the trial to them. If the patient agrees to be contacted by the research team, their care team member will share their information with a member of the research team via secure message and a member of the team will reach out via the participant's preferred method of communication (phone, email, etc). Due to the COVID- 19 pandemic and the fact that diabetes is a risk factor for the virus, all participants will undergo the informed consent process remotely. The research team will make contact with the participant via the mechanism shared with them by the treating team, introduce the project and ask if the participant would like to undergo the informed consent process via an online REDCap survey (screenshots attached) or via a paper consent form sent in the mail. The research team member will then send the Informed Consent Form (ICF) to the participant via either a URL by email or a paper ICF by mail. The research team member will set up a time to discuss the ICF with the participant either by phone or video chat and will describe the study to the participant, review the risks and benefits outlined in the study consent form and address any questions from the participant before asking them for their consent to participate in the study. After consent is obtained, participants will complete an intake survey ("Participant Information Survey") and will be randomized to either the intervention or control group. All participant information obtained during enrollment will be stored securely in a HIPAA-compliant and PHIsafe Stanford Medicine Box folder.

Device setup:

After consent is obtained, the participant's treating physician will communicate their desired insulin protocol with the research team. The information communicated will include the following:

- Starting insulin prescription
- Goal fasting blood sugar
- Titration parameters (e.g. Increase starting dose by 2 units every 3 days if not at goal fasting blood sugar)
- Situations in which they would want their patient to contact their provider or seek immediate medical attention and call 911/report to an ER.

This information will be communicated with the research team via either a custom Epic order set currently in development or a secure online portal developed by the research team. The provider will only have to provide the patient's unique study ID in order to enter this information in the portal. This ID will be securely emailed to the provider upon enrollment of the patient. The provider will be asked to confirm their prescription inputs via the secure online portal to reduce the probability of erroneous data insertion. The provider will also have to confirm the ID of the patient to prevent the provider from erroneously placing a prescription for the wrong patient. No identifying information will be collected by the portal. For participants in the intervention group, this information will be programmed into the digital voice assistant application. For participants in the control group, this information will be recorded for future data analysis.

Intervention group:

Due to the COVID-19 pandemic and the fact that diabetes is a risk factor for the virus, we will mail devices to participants in the intervention group. We will also provide them with the option to set up a phone call or video chat with a member of the research team to help them with device set up.

Device setup will include the following steps:

- Open Alexa Echo Dot package and plug in to power
- Downloading the "Alexa" smartphone application
- Through the Alexa smartphone application, enabling our custom application (called an "Alexa Skill").
- Logging in to our custom application with a unique study ID that is linked to the participant's insulin protocol.

A detailed document called "Alexa Setup Instructions" will be provided to subjects that go into granular detail on how to set up the device as well as its functionalities (screenshots attached).

The entire set up process should take about 5-10 minutes.

Control groups:

For participants in the standard of care control group, we will email them a copy of a blood sugar and medication administration log for them to fill out electronically through REDCap or print and fill out ("Blood Sugar Log"). If a participant doesn't have access to a printer, we will mail them a copy of the log.

As an additional control, a subset of patients receiving the voice assistant device will also be given a blood sugar and medication administration log and will be asked to use both the voice assistant and the blood sugar and medication administration log for 2 of the 8 weeks they are participating in the trial ("Blood Sugar Log - 2 weeks only")

Data collection:

Data will be collected daily from participants in the intervention and control groups of the study. Participants in the intervention group will be able to interact with our custom app by speaking with their Echo Dot. Participants will be instructed to "check in" with the app once daily at which point the app will collect information about recently checked blood sugars and recent administration of insulin. Data collected by the device will be read back to the patient for confirmation. At the end of the check in, the app will remind patients about the details of their insulin regimen. Based on the patient's self-reported data, this reminder might include a prompt to change the dose of their insulin. All reminders and prompts will be strictly based on the physician-prescribed insulin protocol at the beginning of the study, and prompts will include a summarization of the rationale behind the recommendation (e.g. "Your fasting blood sugars are still above goal. Based on your prescribed treatment plan, you should increase your dose of Lantus to 17 units."). No automated decisions will be made by the voice assistant. The voice assistant will only be assisting the patient with instructions that patients are normally given in writing by their provider.

An instruction manual will be provided to the patient with details on how to interact with the device ("Alexa Setup Instructions"). The only data collected from the patient will be patient-reported blood sugar data and medication administration occurrences. The audio data collected by the device is encrypted and sent to the Amazon cloud for processing into relevant text. The text data is supplied to our application for analysis and storage. Our application will not receive or store any audio data. No protected health information will be collected by our app. All data will be de-identified and stored in the Amazon Web Services cloud. All data will be linked to a participant's unique study ID. A document linking a participant's unique ID to their name and medical record number will be stored on the secure PHI-safe Stanford Medicine Box server.

Patients in the control group will use their provided log, labeled with their unique study ID, to record their daily blood glucose checks and insulin adherence. This is part of the standard of care in patients with insulin-dependent diabetes. At the end of the trial period, we will collect this log from patients for data analysis. Participants can choose to securely email or upload this log to the research team through REDCap, or if they prefer, they will be provided with a pre-paid envelope to mail the log free of cost.

Finally, user satisfaction survey data will be collected at the beginning and end of the study from patients in the intervention and control groups. The first survey will include "Problem Areas in Diabetes" ("PAID") questions validated in the literature as a rapid screen for diabetes-related emotional distress (<https://pubmed.ncbi.nlm.nih.gov/19841892/>). This survey is labeled "Diabetes Attitudes (PAID) Survey" (screenshots attached). The second survey will include questions specifically tailored towards interrogating the patient's attitude toward and comfort with insulin dose adjustments ("Medication Adherence Survey"). The third and final survey will include questions on attitudes towards healthcare technology ("Health Technology Survey"). All surveys will be collected online via REDCap.

Data analysis:

Members of the research team will review the collected blood sugar and insulin administration data for analysis. Specifically, we will analyze the collected blood sugar data to determine how often blood sugars were checked and how well-controlled they were. We will also analyze insulin administration data to determine how adherent participants were to their prescribed regimen and how effectively participants were able to titrate their insulin to an effective dose. We will also analyze study survey data to assess participant's diabetes selfefficacy and attitudes towards healthcare technology.

In addition to reviewing data collected by our app and REDCap, the research team will also access the medical record of participants who have completed the trial to obtain certain lab results and medication data to help supplement any missing data from the trial. Specifically, the research team will obtain recent blood sugar and Hemoglobin A1c values, as well as the most recent insulin prescription. This will help the research team perform data analysis in cases where trial data are incomplete. Please note that this is only for participants who have been consented, enrolled and have completed the full 8 weeks of the trial.

If participants decide to withdraw from the study, they can do so at any time by contacting [name] at [contact] or [contact]. After study completion, participants will be able to keep their Amazon Echo device for personal use. Their specific login ID will be disabled which will preclude them from using our custom application after study completion. If participants decide to withdraw from the study before completion, they will be asked to return their Amazon Echo device. They will be provided with pre-paid packaging to do so.

Infection control strategies implemented to ensure the safety of the research staff/faculty who will come to campus and to mitigate risks to them and their families:

1. Personnel are trained on the need to stay home and get tested if they have a new cough, fever, difficulty breathing, chills, muscle pain, headache, sore throat, recent loss of taste or smell.
2. All research staff/faculty will follow Stanford's social distancing protocol, which includes:
 - a. Maintaining physical distancing.
 - b. Use of face coverings and eye protection.
 - c. Frequent handwashing and use of hand sanitizer.
3. Researchers and support staff returning to campus will be required to use the Health Check tool to report health status each day.
4. There will be no participant-facing research staff as the informed consent and patient enrollment process will be conducted virtually.

Infection control strategies implemented to ensure the safety of the research participants:

1. All devices will be cleaned prior to being mailed to the participant.
2. Participants will perform self-setup of their device to avoid the need for an in-person visit with research staff.

b. Procedure Risks

This study poses minimal risk to its participants. Patients in the control group will receive standard of care management of insulin-dependent diabetes. Patients in the intervention arm will not be subject to any risky treatments. They will be interacting with a digital tool that will collect information and remind them of their physician-prescribed treatment plan. The digital tool will not make any autonomous medical decisions or alter the physician's plan in any way. All data collected by the digital tool is anonymized. The voice assistant device will confirm the patient's self-reported data with readback to the subject and verbal confirmation by the subject, prior to storing the data. If a blood sugar reading is outside a standard safe range as determined by their physician, the voice assistant device will provide them the same instructions that would be provided on written instructions by their provider. For example, if a patient's reported blood sugar is less than 70, the voice assistant may notify the subject that their doctor has instructed at such blood sugars to consume something sweet and recheck their sugar. If a patient's reported blood sugar is greater than 350, the voice assistant may notify the patient that their doctor has instructed at such blood sugars to notify a medical professional immediately. If a patient's sugars are dangerously hypoglycemic or dangerously hyperglycemic as determined by their provider, the device will inform the patient to seek medical attention immediately and report to an ER/call 911 per their provider's instructions.

c. Use of Deception in the Study

No deception strategy will be used in this study.

d. Use of Audio and Video Recordings

Amazon Echo devices (and all similar voice assistant technologies) record audio during user interactions. This audio data is encrypted and sent to the Amazon cloud for processing into relevant text. The text data is supplied to our application for analysis and storage. Our application will not receive or store any audio data. All audio data collected by Amazon Echo devices are visible in the Alexa app for users to see and delete. Furthermore, Amazon explicitly states that its devices do not record audio data when users are not interacting with its devices. Whenever an Amazon Echo device is recording audio data, a special indicator light will turn on to alert the user. These details will be included in the informed consent process and patients will be instructed on how to delete audio recordings in their Amazon privacy settings if desired.

e. Alternative Procedures or Courses of Treatment

There are no other alternative procedures for collecting data from a digital voice assistant in a patient's home. No standard treatments will be withheld from participants. The alternative is not to participate in the study.

f. Will it be possible to continue the more (most) appropriate therapy for the participant(s) after the conclusion of the study?

Yes.

g. Study Endpoint(s)

We will be evaluating the end points every 2 weeks for 8 weeks. The clinical end points we will be monitoring are blood sugars obtained through standard of care treatment. The study will not be terminated early for any foreseeable reason. The study will end after two months of data collection per patient. During the two months of data collection, the treating physician will be able to make changes to the patient's insulin regimen at any time but logging into our secure research portal. These changes will be reflected instantly in our Alexa application.

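### Randomisation does not wait for the physician's initial insulin settings, so those settings could be chosen with the arm known

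*Protocol*

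**What the plan says.** Under Recruitment process in Protocol section 2a, consented participants complete an intake survey "and will be randomized to either the intervention or control group". Under the next heading, Device setup, the protocol says: "After consent is obtained, the participant's treating physician will communicate their desired insulin protocol with the research team". The physician supplies a starting prescription, a fasting glucose goal, titration parameters (the example is "Increase starting dose by 2 units every 3 days if not at goal fasting blood sugar") and the situations in which the patient should seek help.

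Two routes are offered: an Epic order set still in development, or a secure portal. Portal entry needs the study ID: "This ID will be securely emailed to the provider upon enrollment of the patient". The provider confirms the inputs, and the stated reason is to avoid entry errors. The settings then go into the app for the intervention arm. For the other arm: "For participants in the control group, this information will be recorded for future data analysis".

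On their use, the Data collection text says: "All reminders and prompts will be strictly based on the physician-prescribed insulin protocol at the beginning of the study". Section 2g lets the treating physician change the regimen at any time in the two months. Section 4a describes a default titration protocol and provider-set limits on the algorithm. Section 1a names outcomes "such as medication adherence, blood sugar control and time to optimal insulin dose".

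**The concern.** The physician's entry helps determine the outcome. The fasting goal and the titration step bear on how fast a patient reaches a stable dose and how early glucose falls. In the app arm the prompts follow the entry; in the control arm the patient follows the physician's own instructions. The limits in section 4a act on the algorithm, so they operate only in the app arm.

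A physician who knows that an algorithm with limits will guide titration might choose differently for that patient than for one using a log. The choice could be bolder or more cautious. Part of any arm difference in time to optimal dose, or in early glucose control, would then reflect the physician's choice and not the device.

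Recording the settings does not repair this afterwards. Settings chosen after allocation may themselves be affected by the arm, so they cannot be adjusted for as baseline values.

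**Working it through.** **1. Order of the steps.**
- Randomisation: follows consent and the intake survey. No other condition is stated.
- Physician's settings: follow consent. No order relative to randomisation is stated; they appear under the later heading.
- Portal entry: needs the study ID, sent on enrolment, so it cannot precede enrolment. Whether enrolment includes randomisation is not said.
- Epic route: no study-ID step is described, so nothing can be inferred about its timing.
- Confirmation: a check on data entry, not a condition for releasing the allocation.
- Withholding the arm from the physician: not described anywhere.

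The text therefore permits entry either before or after the arm is known.

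**2. The SAP's figure.** Inputs from the SAP: 84% vs 40%, 80% power, two-sided alpha 0.05. Equal allocation is assumed because no ratio is given. With the unpooled normal approximation, n per arm = (1.96 + 0.8416)² × (0.84 × 0.16 + 0.40 × 0.60) / 0.44² = 15.18, rounded up to 16, or 32 in total. This reproduces the SAP. The figure is not in dispute; it gives the arm sizes used in step 4 (16, or 25 if all 50 are recruited).

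**3. Sensitivity of time to dose (illustration, not an estimate of bias).** From the documents: steps of 2 to 4 units (section 7a) and a 3-day interval (the section 2a example). Assumed: each patient has one fixed step of 2 or 4 units; the needed increase is 20 units (range 12 to 28); every scheduled step is taken; the arms differ by 25 points in the share given the larger step (range 10 to 50).

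Days to dose = 3 × (need / step). Mean shift = share difference × gap.

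| Need | 2-unit step | 4-unit step | Gap | Shift at 10 / 25 / 50 points |
|---|---|---|---|---|
| 12 | 18 days | 9 days | 9 | 0.9 / 2.25 / 4.5 days |
| 20 | 30 days | 15 days | 15 | 1.5 / 3.75 / 7.5 days |
| 28 | 42 days | 21 days | 21 | 2.1 / 5.25 / 10.5 days |

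If only 75% of steps are taken in both arms (assumed), a 20-unit need takes 30 / 0.75 = 40 days or 15 / 0.75 = 20 days. The gap is 20 days and the shifts are 2.0 / 5.0 / 10.0 days.

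**4. Could a by-arm table reveal it?** Take 62.5% vs 37.5% given the larger step, a 25-point difference. SE = √(2 × 0.375 × 0.625 / n).
- n = 16: SE 0.171; 95% CI 25 ± 33.5, or −8.5 to 58.5 points.
- n = 25: SE 0.137; 95% CI 25 ± 26.8, or −1.8 to 51.8 points.

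Both intervals include zero, so a moderate imbalance could not be told from chance.

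**5. Does the illustration reach the powered outcome?** The slowest modelled patient (28 units, 2-unit step, 75% of steps) takes 42 / 0.75 = 56 days, exactly 8 weeks. Every modelled patient reaches the dose within follow-up. The model changes speed, not the proportion controlled at 8 weeks.

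**The case against.** The strongest reply is that this argues from silence. Both steps are tied to consent under separate headings, so the order of description need not be the order of events. Section 2a gives one procedure and one list of settings for everyone, and the arms diverge in the text only after entry and confirmation. The study ID is randomly generated (section 8), and nothing links it to the arm. This stands. A reader might infer that physicians know the arm when they enter the settings, but the documents do not say so, and entry before allocation fits the text equally well. What remains is that nothing prevents the other order.

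Second, several features narrow the problem: a default protocol exists, some patients are already on insulin, and settings are recorded in both arms. This stands in part. Physicians still enter their own desired protocol, and recording shows a difference without preventing it.

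Third, the physician's response to the app may be part of the intervention, so isolating the device is a preference. The documents do not settle this, although section 1 frames the question as one about the voice assistant.

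Fourth, open choice of regimen continues under section 2g, so any protection is partial. That is correct.

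**Conclusion.** The point holds as a minor one. As written, allocation does not wait for the initial settings and the arm is not withheld from the person choosing them. The possible bias falls mainly on time to optimal insulin dose and early glucose control. Its direction and size cannot be derived from the documents. The shift of 3.75 days, with 0.9 to 10.5 days across the on-schedule scenarios, rests wholly on the assumed need, the assumed arm difference, a fixed step and an interval given only as an example. It models the step alone, not the fasting goal or the starting prescription.

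Two stronger readings are not supported. A reader might infer that the powered comparison of glycaemic control at 8 weeks is compromised, but the illustration does not move that proportion. A reader might also infer biased adherence, but section 2a assesses adherence against each participant's own prescribed regimen, so different settings need not shift it, and no calculation shows that they would.

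**What to change.** In section 2a, state that allocation is generated and released only after the provider has entered and confirmed the insulin protocol, whichever route is used. The confirmation is described for the portal, so the Epic order set needs an equivalent step. Time-stamp the confirmed entry in both arms. Report the initial settings by arm as a description, not as a test for bias. No clinical setting changes, and the sample size is unaffected.

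The cost is a wait for the provider's entry, of a length the documents do not give, plus a time stamp and one table of data already collected. The gain is that the initial settings become true baseline values. Later changes remain at the physician's discretion and can be reported by arm only as far as the portal captures them. The medical record cannot fill that gap: it supplies only the latest insulin prescription, and of record access the protocol says "this is only for participants who have been consented, enrolled and have completed the full 8 weeks of the trial".

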8. BENEFITS

PHI will only be collected once during enrollment, which includes an entry survey on REDCap (screenshots attached). The least amount of information will be obtained to accomplish the purpose of the research. This data will be stored securely in a folder on the HIPAA-compliant Stanford Medicine Box. A unique study ID will be randomly generated for each patient (not derived from any identifiable information). This ID will be used with our application and will be linked with the self-reported patient data that we collect using the Amazon Echo Dot. No PHI will be collected or stored by our application on the Amazon Echo Dot.

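### On the portal route, the only wrong-patient check described is confirmation of a random study ID, and no described step has the participant confirm the loaded insulin plan

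*Protocol*

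**What the plan says.** Protocol section 2.a (Device setup) gives two routes for the treating physician's insulin plan: an Epic order set still in development, or a secure portal built by the research team. This point concerns the portal only.

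- **Entry.** "The provider will only have to provide the patient's unique study ID in order to enter this information in the portal". The ID reaches the provider by secure email when the patient enrolls.
- **Checks at entry.** The provider confirms the prescription inputs, to guard against data-entry error. The provider must also "confirm the ID of the patient to prevent the provider from erroneously placing a prescription for the wrong patient".
- **Identifiers.** "No identifying information will be collected by the portal". Section 8 adds that the ID is generated at random and carries nothing identifying.
- **Link to the device.** The participant logs in to the app with the study ID, and the plan held under that ID drives the prompts.
- **Later edits.** Section 2.g lets the physician change the regimen through the portal at any time. "These changes will be reflected instantly in our Alexa application".
- **Participant confirmation.** Section 2.a (Data collection): "Data collected by the device will be read back to the patient for confirmation". Section 2.b: "The voice assistant device will confirm the patient's self-reported data with readback to the subject and verbal confirmation by the subject".
- **Regimen reminder.** Each check-in ends with the app stating the regimen, and "this reminder might include a prompt to change the dose of their insulin".

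**The concern.** The protocol itself names the hazard of a prescription placed for the wrong patient, but the control it describes is confirmation of an arbitrary code. That may catch a typing slip. It gives the provider nothing by which to recognise the patient.

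An intervention participant whose ID held someone else's plan would be prompted toward that person's dose, fasting goal and titration step. The situations for contacting the provider or calling 911 are communicated with the same plan, so they would be the other patient's too. Because the tool prompts insulin doses at home, an error in either direction could matter clinically.

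**Working it through.** The plan gives no figure on this point, so the check sets the provisions side by side.

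**1. What confirming the ID can detect.** If the provider mistypes an ID, comparing it with the emailed one may reveal the slip. If the provider picks the wrong one of two emailed IDs, the entry is valid and agrees with the email it came from. With a random ID and a portal that collects no identifying information, nothing described would prompt the provider to notice. Confirming the prescription inputs does not help, because they may be exactly what the provider meant to enter, for a different patient.

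**2. Who is exposed.** Each ID goes to that patient's own provider, so the error arises mainly for providers with two or more participants. Restricting each login to the provider's own patients would not remove it.

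**3. Edits.** Section 2.g names no check before a change goes live.

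**4. What participants confirm.** Confirmation is described in four sections:

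- 2.a (Data collection): data collected by the device.
- 2.b: self-reported data.
- 4.a: steps when reporting data.
- 7.a: self-reported values before they are logged.

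Sections confirming the loaded plan: 0 of 4. This counts text; it does not measure risk.

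**5. What the other safeguards do.**

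- *Regimen reminder (2.a) and dose read-back (7.a).* These are real cues. One 7.a example gives both the new dose, 17 units, and the previous one, 15. No answer is requested, and someone just starting insulin may have no established dose for comparison.
- *Small steps (7.a).* Adjustments of 2 to 4 units bound each change, not the gap between two patients' starting doses.
- *Maximum dose (4.a).* The provider sets it, so if it is entered with the plan it may be the wrong patient's cap.
- *Hypoglycemia protocol (4.a).* It is described as covering a starting dose set too high in error. It limits harm but does not identify a wrong plan.
- *Upward titration (2.a) and hyperglycemia alerts (2.b).* These act if the dose is too low, but the goal and thresholds they use could be misassigned with the plan.
- *Chart review (2.a, Data analysis).* It is limited to participants who completed all 8 weeks, so it is not an early check.

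**6. Burden of a plan confirmation.** Check-ins = 8 weeks × 7 days = 56. Read-outs = 1 + k, where k is the number of portal edits. As a share of check-ins this is (1 + k)/56. With k = 0 it is 1/56 = 1.8%, and each edit adds another 1.8 percentage points. The protocol sets no limit on k, so there is no upper bound to quote.

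**7. Frequency of the problem.** This cannot be derived. The documents give neither an entry-error rate nor the number of providers with several participants.

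**The case against.** The strongest reply is that the outcome depends on material not in the supplied text: the portal screens, the scope of a provider's login, and the Alexa Setup Instructions, which the protocol describes as detailed. A check could sit in any of them. This stands as a limit: the documents show that no such step is described, not that none exists. If one does, the sponsor need only state it.

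Second, the existing protections are real. The provider confirms twice, and the app states the regimen daily. At the protocol's example interval of 3 days between increases, the first reminders would normally precede the first titration prompt, so an alert participant could spot a mismatch. This also stands, but it relies on the participant volunteering a doubt that nobody has asked about, and it helps less after an instant edit.

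Third, a reader might infer that a plan set too low has no safeguard. The documents do not support that: titration raises the dose when fasting glucose is above goal, and section 2.b describes alerts for high readings. Those protections would be weakened by a wrong plan, not absent.

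Fourth, a participant read-back is one remedy among several. Research staff could instead match the ID to the chart using the link file. That is more direct, but it takes staff time at each entry, and chart access before completion is outside what section 2.a allows.

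**Conclusion.** The point holds as a gap in the described safeguards on the portal route. Confirming a random ID may not catch a plan or edit placed under another valid ID held by the same provider, and no described step has the participant confirm the loaded plan. The partial safeguards reduce the consequences but do not ask the question.

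A reader might infer that misassigned plans are likely, or that the portal would accept any participant's ID from any provider. The documents support neither: frequency is unknown and login scope is not described. No effect on the endpoints or the analysis is claimed.

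The conclusion rests on two assumptions: that some providers have more than one participant, and that the materials not supplied contain no further check. The case for acting is that the remedy is cheap and protects patients using an insulin-dosing tool.

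**What to change.** **Change.** In the intervention arm, at first login and after each portal edit, before any dose prompt, the app reads out the insulin name, current dose, fasting goal and titration step held under that ID. The participant answers yes or no against their own prescription or the physician's latest instruction. A *no* holds titration prompts and goes to the research team, which holds the file linking IDs to patients, and to the treating physician. What the participant takes meanwhile remains the physician's decision.

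Amend the sentence in section 2.a (Data collection) that limits what is collected from the patient, so that this answer may be recorded. Softening the Device setup wording, so that ID confirmation is said to reduce the chance of a wrong-patient entry and not to prevent it, is editorial and optional.

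**Cost.** Minor app programming and testing, a procedure for handling a *no*, one short read-out at login plus one per edit, and occasional false *no* answers to resolve. It needs no visit and no new identifying data.

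**Limits.** It does not cover control-arm entries. Nor does it alert the intended patient of a misdirected edit, because nothing changes under that patient's ID.
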